9.4.4 SAFETY ANALYSES

We will report results using descriptive statistics (including frequency distributions, a measure of central tendency and a measure of dispersion) average VRISE scores.

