8.2 ADVERSE EVENTS AND SERIOUS ADVERSE EVENTS

Safety will be assessed by adverse events (AEs), premature withdrawals for AEs, rates of AEs.

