8.2.2 DEFINITION OF SERIOUS ADVERSE EVENTS (SAE)

An Adverse Event (AE) is any untoward medical occurrence associated with the use of an intervention in a study participant, which does not necessarily have a causal relationship with the intervention. An AE can therefore be any unfavourable and unintended sign (including an abnormal laboratory finding), symptom or disease temporally associated with the use of the intervention, whether or not considered related to the investigational intervention.

Stable chronic conditions which are present prior to entry in the study and do not worsen are not considered AE. These pre-existing conditions will be documented in the participant's medical history.

AEs will be the primary safety endpoints. Known AEs induced by IVR stimulation are nausea, dizziness and disorientation. The severity of these AEs will be scored using the validated VRISE questionnaire. A VRISE score < 25 is considered as an AE. Three (3) consecutive VRISE scores < 25 will lead to the withdrawal of the study.

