8.2.3 CLASSIFICATION OF AN ADVERSE EVENT

VRISE questionnaire for assessing AEs related to audiovisual IVR stimulation will be recorded electronically (.csv file) after each home-based session (every 2 days) and sent through Wi-Fi to a dedicated and secured laboratory computer in real-time.

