8.2.4 TIME PERIOD AND FREQUENCY FOR EVENT ASSESSMENT AND FOLLOW-UP

All Adverse Events (AEs) or Serious Adverse Events (SAEs) due to IVR stimulation resolve as soon as the stimulation stops²⁵. Investigators will follow-up the participant at 24 hours by phone or email assessing the severity of the AEs using the VRISE questionnaire

AE reporting will begin at the time of signing of the informed consent (screening) and will continue until discharge from the study. AEs will be elicited by:

- spontaneous report by participants and/or parents,
- by 3 consecutive VRISE scores < 25,
- by observation (by the investigators and/or healthcare staff).

AEs will be documented in the source documents and the eCRF within 24 hrs.

All AEs and SAEs occurring while on study must be documented regardless of relationship. Information to be collected includes event description, date and time (if possible) of onset, date and time (if possible) of resolution/stabilization of the event, outcome, and the assessment of seriousness, expectedness, relationship to study intervention and severity by a delegated qualified physician.

Any baseline condition recorded in the medical history that deteriorates at any time during the study, will be recorded as an AE or SAE.

Changes in the severity of an AE will be documented to allow an assessment of the duration of the event at each level of severity to be performed.

Events will be followed for outcome information until resolution or in the opinion of the PI or qualified physician delegate, the participant is stable and does not require further follow-up, or the participant is deemed lost to follow-up.

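### A single VRISE score below 25 is defined as an adverse event, but the elicitation list names only three in a row, and section 9.4.4 plans averages with no adverse event count or rate

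*Combined protocol and SAP*

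**What the plan says.** **Definition.** The adverse event definition text, printed under heading 8.2.2, says "AEs will be the primary safety endpoints" and "A VRISE score < 25 is considered as an AE". It sets no limit on when the score is taken. Three consecutive low scores have a different role there: withdrawal. Sections 7.2 and 8.2.3.1 also use three in a row as the rule for ending the intervention or withdrawing.

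**Elicitation.** Section 8.2.4 lists three routes by which adverse events come to light: "spontaneous report by participants and/or parents", "by 3 consecutive VRISE scores < 25", and observation by investigators or staff. The same section adds: "All AEs and SAEs occurring while on study must be documented regardless of relationship".

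**What safety consists of.** Section 8.2: "Safety will be assessed by adverse events (AEs), premature withdrawals for AEs, rates of AEs". Section 9.3 defines a Safety population of registered participants with at least one training session.

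**Analysis.** Section 9.4.4 in full: "We will report results using descriptive statistics (including frequency distributions, a measure of central tendency and a measure of dispersion) average VRISE scores".

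**Timing of scores.** Sections 3 and 4.1 have VRISE completed before and after each session. Section 8.2.3 describes adverse event assessment from scores recorded after each home session. VRISE is also used at inclusion (section 5.2) and at the 24-hour follow-up (sections 7.2 and 8.2.4).

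**The concern.** There are two gaps.

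1. **Classification.** The definition turns on one low score, while the only VRISE trigger in the elicitation list is the run of three that serves elsewhere as the withdrawal rule. Staff working from the list would have no listed VRISE prompt to record an isolated low score as an adverse event.
2. **Reporting.** Section 8.2 promises events, rates and withdrawals for adverse events, but the safety analysis text carries none of them forward. This gap remains whichever counting rule is chosen, because a mean above 25 is compatible with many scores below 25.

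At stake is the tolerability picture in children, for whom the protocol says (text printed under heading 7.3) that this home-based approach is untested. The report could look more favourable than the protocol's own definition of an adverse event supports.

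**Working it through.** The plan states no adverse event rate and no figure to reproduce. The text comparison carries the point; the arithmetic only shows how far apart the two triggers can be.

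**Inputs from the documents:** 10 children (section 9.2); 15 sessions (section 4.1), so 15 post-session scores per child; five items scored 1 to 7 (section 4.1); threshold 25.

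**Assumptions:** the VRISE score is the sum of the items, so it runs from 5 to 35; the chance p that a score is low is 5%, 10%, 20% or 30%; the within-child correlation rho is 0, 0.3 or 0.5. The documents give none of these.

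**Formulas, per child with n = 15 scores:**
- At least one low score: 1 − (1 − p)^15. For p = 0.05 this is 0.537, or 5.4 of 10 children.
- A run of three: exact recursion on the current run length, absorbing at three. For p = 0.20 this is 0.083, or 0.8 of 10 children.
- Clustering: each child's p is drawn from a beta distribution with mean p and intraclass correlation rho (parameters p(1/rho − 1) and (1 − p)(1/rho − 1)), and both probabilities are averaged over it.

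**Expected children out of 10 (at least one low score / a run of three):**

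| rho | p = 5% | p = 10% | p = 20% | p = 30% |
|---|---|---|---|---|
| 0 | 5.4 / 0.0 | 7.9 / 0.1 | 9.6 / 0.8 | 10.0 / 2.4 |
| 0.3 | 2.3 / 0.4 | 4.1 / 0.8 | 6.6 / 1.9 | 8.1 / 3.2 |
| 0.5 | 1.5 / 0.5 | 2.9 / 1.0 | 5.0 / 2.1 | 6.6 / 3.2 |

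Counting pre-session scores as well gives n = 30. At p = 5% and rho = 0.3 the pair becomes 2.85 / 0.55, so the gap widens from 2.29 − 0.38 = 1.9 children to 2.85 − 0.55 = 2.3.

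**What an average can mask:**
- Five scores of 20, never three in a row, and ten of 30: (5 × 20 + 10 × 30)/15 = 26.7. The mean is above 25, yet there are five adverse events by the definition.
- At most 10 of 15 scores can be low without a run of three (two low, one not, repeated). With those at 24 and the rest at 35: (10 × 24 + 5 × 35)/15 = 27.7, again above 25.

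**The case against.** The best reply is that the text largely settles the classification question. Section 8.2.4 says how events are elicited and does not redefine them. Read with the definition, its duty to document every adverse event covers a single low score. Every score reaches the laboratory electronically, so nothing is lost, and investigator observation might be taken to include reviewing those scores, although the protocol does not say so. A reader might infer that the protocol has narrowed its definition to three in a row, or that isolated events will disappear. Neither follows. What stands is that a general duty sits beside a narrower trigger list, and staff are not told that one score starts the process.

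On reporting, section 8.2 already commits to rates and withdrawals, section 9.4.5 has a general line on categorical endpoints, and VRISE scores also appear among the primary feasibility measures (section 3, and section 7 for withdrawn patients). The sentence in 9.4.4 also lacks a connecting word. If its frequency distributions apply to individual scores, values below 25 would be visible: in the 26.7 example the SD is about 4.9 and a third of the scores are low. This softens the point without removing it. On no reading does 9.4.4 name an adverse event count, a rate or withdrawals, and the line in 9.4.5 names no adverse event summary.

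The table might be taken as the most that the list could miss. It is not. It counts children over post-session scores only, grows if pre-session scores count, and ignores isolated low scores in a child who also has a run. In the other direction, spontaneous report and observation would catch some events.

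**Conclusion.** The point holds as two linked inconsistencies: the definition and the elicitation list use different VRISE triggers, and the safety analysis does not carry through the measures that section 8.2 names. The likely harm is under-classification and an incomplete safety summary, not lost data.

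In the illustration the single-score trigger picks out at least twice as many children as the run of three in every scenario; at rho = 0.3 it is 2.3 to 8.1 against 0.4 to 3.2 of 10. These sizes rest entirely on the assumed rates, correlations and number of scores. The masking examples rest on the assumed summed score.

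Which timings count is an open ambiguity, not a formality, because the definition sets no limit while section 8.2.3 refers to post-session scores.

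A reader might also infer that the pilot's success decision is affected. It is not: the feasibility criteria use completion, runs of low VRISE scores and cybersickness dropouts, and none uses the adverse event count. Severity is therefore minor to should-fix. Confidence is high for the textual mismatch and lower for any actual distortion of the tolerability picture.

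**What to change.** 1. **Reconcile the definition with section 8.2.4** so that one stated rule governs which VRISE scores count as adverse events. The rule should say which timings count: pre-session, post-session, inclusion and 24-hour follow-up. Which rule to adopt is for the investigators. The threshold and the withdrawal rule are left untouched.
2. **Extend section 9.4.4.** For the Safety population, report the adverse event count and rate under that rule; the number and proportion of children with at least one score below 25, shown separately for pre-session and post-session scores; and premature withdrawals for adverse events. Keep the VRISE averages as a supplement.

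The cost is a clarified sentence and one small table built from scores already transmitted. The reported adverse event count may be higher. If single scores count, each needs the causality and expectedness assessment of section 8.2.3, eCRF entry within 24 hours and follow-up under section 8.2.4, and ethics board reporting as required by section 8.2.5.

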9.4.5 BASELINE DESCRIPTIVE STATISTICS

Summary statistics will be used to describe baseline characteristics and other outcomes of interest. Categorical endpoints will be summarized using proportions and frequencies. Continuous endpoints will be summarized using the mean, median, range or standard deviations.

9.4.6 TABULATION OF INDIVIDUAL PARTICIPANT DATA

Raw data corresponding to primary outcome measures related to IVR stimulation (device ID#, subject #, date/time, time to complete the task/block, number of tasks/blocks performed, total stimulation time, total duration of the session) will be recorded in a digital table (file .csv size = 2 Ko) corresponding to source data. This .csv file, not containing any personal health information nor identification information, will be sent to a dedicated and secured laboratory computer through Wi-Fi and a copy will be stored on the Oculus. Once received on the laboratory computer, these data will be transferred electronically to eCRFs (the original .csv file will be kept on the UHN network and in a separate encrypted and password-secured hard drive in the investigators' office).

Raw data corresponding to secondary outcome measures related to fixation stability will be stored in the device (MAIA microperimeter) and a copy will be transferred electronically to eCRFs through encrypted uhn.ca/uhnresearch.ca emails.

Raw data corresponding to secondary outcome measures related to BCVA, contrast sensitivity, reading speed, visual fields and quality of life will be recorded on dedicated sheet (source document) and transferred manually to eCRFs.

10.1 REGULATORY, ETHICAL, AND STUDY OVERSIGHT CONSIDERATIONS

10 SUPPORTING DOCUMENTATION AND OPERATIONAL CONSIDERATIONS

10.1.1 STUDY DISCONTINUATION AND CLOSURE

This study may be temporarily suspended or prematurely terminated if there is sufficient reasonable cause. Written notification, documenting the reason for study suspension or termination, will be provided by the suspending or terminating party to <study participants, Investigator, funding agency, Sponsor and regulatory authorities>. If the study is prematurely terminated or suspended, the PI will promptly inform study participants, the REB and Sponsor and will provide the reason(s) for the termination or suspension. Study participants will be contacted, as applicable, and be informed of changes to study visit schedule.

Circumstances that may warrant termination or suspension include, but are not limited to:

- Determination of unexpected, significant, or unacceptable risk to participants
- Demonstration of efficacy that would warrant discontinuing the trial
- Insufficient compliance to protocol requirements
- Data that are not sufficiently complete and/or evaluable
- Determination that the primary endpoint has been met
- Determination of futility

Study may resume once concerns about safety, protocol compliance, and data quality are addressed, and satisfy the Sponsor, REB, DSMB, and/or regulatory agency.

10.1.2 CONFIDENTIALITY AND PRIVACY

Participant confidentiality and privacy is strictly held in trust by the participating Investigators, their staff, and the Sponsor(s). This confidentiality is extended to cover testing of biological samples and genetic tests in addition to the clinical information relating to participants. Therefore, the study protocol, documentation, data, and all other information generated will be held in strict confidence.

All research activities will be conducted in as private a setting as possible.

Any research information obtained about the patient in this study will be kept confidential. A patient will not be identified by name, only by unique study ID number. The patient's name or any identifying information will not appear in any reports published as a result of this study. All identifying information will be kept behind 2 security measures or as per equivalent institutional policy, under the supervision of the study/site PI and will not be transferred outside of the hospital.

The study monitor, auditor and other authorized representatives of the Sponsor, representatives of the Research Ethics Board (REB) or regulatory agencies may inspect all documents and records required to be maintained by the Investigator, including but not limited to, medical records and pharmacy records for the participants in this study. The clinical study site will permit access to such records.

Study participant research data, which is for purposes of statistical analysis and scientific reporting, will be transmitted to and stored at the UHN network. This will not include the participant's contact or identifying information. Rather, individual participants and their research data will be identified by a unique study identification number. The study data entry and study management systems used by clinical sites and by UHN research staff will be secured and password protected. At the end of the study, all study databases will be de-identified and archived at UHN

10.1.4 KEY ROLES AND STUDY GOVERNANCE

Data collected for this study will be analyzed and stored at UHN. After the study is completed, the de-identified, archived data will be transmitted to and stored at UHN for use by other researchers including those outside of the study. Permission to transmit data to UHN will be included in the informed consent.

10.1.5 STUDY MONITORING

Monitoring of the trial will be performed to verify that:

- The rights and well-being of participants are protected;
- The reported trial data are accurate, complete, and verifiable from source documents; and
- The conduct of the trial is in compliance with the currently approved protocol/amendment(s), ICH GCP, and local regulations and requirements.

The Sponsor will be responsible for all monitoring activities. Any trial-related duty or function transferred to and assumed by a third party, including monitoring and auditing, will be specified in a clinical trial agreement and oversight provided by the Sponsor.

The monitoring plan for the trial will be documented prior to the activation of the study and include the following;

- Follow risk-based practices,
- Document the rationale for the chosen monitoring strategy,
- Reference the Sponsor's process that will be followed to address situations of non-compliance,
- Describe the monitoring responsibilities of all the parties involved, and
- Outline the data and processes to be monitored.

The site Investigator(s)/delegate(s) will allow direct access to source data/documents for the purposes of monitoring by the Sponsor, and inspection by regulatory authorities, both domestic and foreign (if applicable). It is important that the Sponsor, site Investigator and site personnel are available during monitoring visits and inspections, and that sufficient time is devoted to the process.

Monitoring procedures will be implemented beginning with the data entry system and data checks that will be run on the database will be generated. Any missing data or data anomalies will be communicated to the site(s) for clarification/resolution.

Monitoring reports will be issued after each monitoring visit for review and follow up by the Sponsor, site Investigator, and appropriate management and personnel responsible for trial and site oversight.

10.1.7 DATA HANDLING AND RECORD KEEPING

Auditing of the trial will be performed independently from monitoring to evaluate trial conduct and compliance with the protocol/amendment(s), SOP, ICH GCP and local regulations and requirements.

The Sponsor will be responsible for all auditing activities. Any trial-related duty or function transferred to and assumed by a third party, including auditing, will be specified in a clinical trial agreement and oversight provided by the Sponsor.

The site Investigator(s)/delegate(s) will allow direct access to source data/documents for the purposes of auditing by the Sponsor, and inspection by regulatory authorities, both domestic and foreign (if applicable). It is important that the Sponsor, site Investigator and site personnel are available during audits and inspections, and that sufficient time is devoted to the process.

Auditing reports will be issued after each audit for review and follow up by the Sponsor, site Investigator, and appropriate management and personnel responsible for trial and site oversight.

10.1.6 QUALITY ASSURANCE AND QUALITY CONTROL

We will comply with FDA's ALCOA guidelines to ensure high quality data recording. The delegation of duties log will specify which tasks are delegated to which personnel. Data entered on dedicated source documents will be recorded legibly in black ballpoint pen and signed. Correction fluid or covering labels will not be used.

10.1.7.1 DATA COLLECTION AND MANAGEMENT RESPONSIBILITIES

Data collection is the responsibility of the clinical trial staff at the site under the supervision of the site Investigator. The Investigator is responsible for ensuring the accuracy, completeness, legibility, and timeliness of the data reported.

All paper sheets recording BCVA, contrast sensitivity, reading speed, quality of life, and adherence log sheet will be considered source documents.

All digital tables (.csv files) generated by and recorded from the IVR stimulation program in the Oculus Go will be considered source data.

All digital data recorded by MAIA microperimeter will be considered source data.

All source documents should be completed in a neat, legible manner to ensure accurate interpretation of data.

Where the source data is not collected as part of the participant's medical record, hardcopies of the study visit worksheets will be provided for use as source document worksheets for recording data for each participant enrolled in the study. Data recorded in the case report form (CRF) derived from source documents should be consistent with the data recorded on the source documents.

Study data will be entered into REDCap (Research Electronic Data Capture), a secure, web-based application designed exclusively to support data capture for research studies. REDCap is developed and maintained by a team at Vanderbilt University and licensed free of charge by the Research Institute at UHN. The application and data are housed on servers provided by UHN. These servers are located within UHN secure data center. Local support for REDcap is provided UHN Research IT.

10.1.8 PROTOCOL DEVIATIONS

To enable evaluations and/or audits from Health Canada and/or the Sponsor, the Principal Investigator agrees to keep records, including the identity of all participating patients (sufficient information to link records, CRFs and hospital records), all original signed informed consent forms, copies of all CRFs, source documents, and detailed records of treatment disposition in a secure location for a minimum of 10 years.

If the Principal Investigator relocates, retires, or for any reason withdraws from the study, then the Sponsor should be prospectively notified. The study records must be transferred to an acceptable designee, such as another Investigator, another institution, or to the Sponsor.

10.1.7.2 STUDY RECORDS RETENTION

A protocol deviation is any noncompliance with the clinical trial protocol or Manual of Procedures (MOP) requirements, if applicable. The Principal Investigator will assure that no deviation from, or changes to the protocol will take place without prior agreement from the Sponsor and documented approval from the Research Ethics Board (REB), except where necessary to eliminate an immediate hazard(s) to the trial participants. The noncompliance may be either on the part of the participant, the Investigator, or the study site staff. As a result of deviations, corrective actions are to be developed by the site and implemented promptly. All protocol deviations will be documented; the Principal Investigator will assess each protocol deviation to determine the impact to the patient's rights, safety or welfare, study efficacy and data integrity. If there is any uncertainty regarding the impact of the protocol deviation, the Principal Investigator will consult with the Medical Monitor.

It is the responsibility of the Principal Investigator to use continuous vigilance to identify and report deviations within 5 working days of identification of the protocol deviation, or within 2 working days of the scheduled protocol-required activity. All deviations must be addressed in study source documents and reported to the Sponsor. Protocol deviations must be sent to the reviewing REB in accordance with their policies. The Principal Investigator is responsible for knowing and adhering to the reviewing REB requirements.

